---

**CONFIDENTIAL****COMPLIANCE STATEMENT**

The study will be carried out in accordance with Good Clinical Practice (GCP) as required by the United States (US) Code of Federal Regulations (CFR) applicable to clinical studies (45 CFR Part 46; 21 CFR Part 50, 21 CFR Part 56, and 21 CFR Part 312) and ICH E6; 62 Federal Register 25691 (1997).

## SYNOPSIS

---

**Title:** A Multi-center, Randomized, Double-Blind, Parallel-group, Vehicle-Controlled Study to Evaluate the Dose-Response Relationship of the Efficacy and Safety of Two Concentrations of DFD-07 (celecoxib) Cream, in Subjects with Actinic Keratosis (AK) of the Face and/or Scalp Over a 12-week Treatment Period

---

**Sponsor:** [name] Ltd.  
[name]  
[name]  
[name],  
Telangana, India

---

**Study Centers:** 20 **Number of Subjects:** 240

---

**Study Treatment:** 12 Weeks **Clinical Phase:** Phase 2b

---

**Objectives:**

---

The objective of this study is:

To evaluate the dose response relationship of the efficacy and safety of two strengths, of topical DFD-07 (celecoxib) Cream, 1.25% and 2.5% when used once or twice daily compared to Vehicle in the treatment of AK of the face and/or scalp over a 12-week period with a 4-week follow up.

---

**Methods:**

---

This is a multi-center, randomized, double-blind, parallel group, Vehicle-controlled study. The study products will be applied to the target lesions once or twice daily for a duration of 12 weeks of treatment, with a 4-week treatment-free follow-up. Subjects, who are at least 18 years old, diagnosed with AK of the face and/or scalp will be randomized to treatment in one of the following four arms (60 subjects in each group):

Treatment Group	Dose Strength	Dose Duration	DFD-07 Cream		Vehicle Cream	
			AM	PM	AM	PM
1	1.25%	12 Weeks	-	✓	✓	-
2	2.5%	12 Weeks	✓	✓	-	-
3	2.5%	12 Weeks	-	✓	✓	-
4	Vehicle	12 Weeks	-	-	✓	✓

The study consists of three phases: Screening (up to 60 days), Treatment (12 weeks) and Follow-Up (4 weeks). In Groups 2 and 4, the randomized investigational products will be applied twice daily for 12 weeks to cover the entire single contiguous 5 cm x 5 cm (25cm^2) lesional area on the face and/or scalp. In Groups 1 and 3, the randomized active product will be

applied only in the evening, while the Vehicle will be applied in the morning to keep the blinding between groups.

Subjects in all the groups will undergo a further 4-week treatment-free period from Week 12 to Week 16 (End of Study).

Subject visits are scheduled at Screening (Visit 1), Baseline (Visit 2 - Day 1), and Weeks 4 (Visit 3), 8 (Visit 4), 12 (Visit 5) and 16 (Visit 6). Clinical determinations of efficacy will be conducted based on clinically visible or palpable lesions of AK in the treated areas at Weeks 4, 8, 12 and 16 in comparison to Baseline. Comparisons will be made between the different strengths and dosing regimens of DFD-07 (celecoxib) Cream and Vehicle Cream.

Local cutaneous tolerability will be determined at Baseline (Visit 2 –Day 1) and visits 3 – 6 for all treated areas. Other safety assessments include physical examinations (HEENT, lungs, heart, abdomen, skin, neurologic) laboratory assessments, electrocardiogram (EKG), vital signs (blood pressure, pulse rate), urine pregnancy tests, and collection of adverse event data.

---

**Number of Subjects:**

---

A total of approximately 240 subjects with actinic keratosis of the face and/or scalp will be randomized into four groups in a 1:1:1:1 ratio (60 subjects in each group) at approximately 20 centers.

---

**Diagnosis and Criteria for Inclusion / Exclusion:**

---

**Inclusion:**

1. Subject understands the study procedures, is willing to comply with the study procedures and required visits, and agrees to participate by giving written informed consent. Subjects with a legal guardian, must have the written informed consent of the legal guardian.
2. Subject (or legal guardian) must be willing to authorize use and disclosure of protected health information collected for the study.
3. Subjects must have 5 or more AK lesions that are non-hypertrophic and non-hyperkeratotic contained within a single contiguous approximate 5 cm x 5 cm (25 cm^2) region of face and/or scalp.
4. Subjects must be 18 years of age or older. Male and female subjects can be enrolled.
5. Female subjects of childbearing potential must agree to use contraception during the study which can include abstinence with an adequate secondary option should the subject become sexually active. All women of childbearing potential must complete a urine pregnancy test (test must have a sensitivity of at least 25mIU/ml for human chorionic gonadotropin) at the Baseline Visit (Visit 2) and the test result must be negative to be eligible for enrollment.

A female is considered of childbearing potential unless she is:

- postmenopausal for at least 12 months prior to study product administration;
- without a uterus and/or both ovaries; or has been surgically sterile (i.e., tubal ligation) for at least 6 months prior to study product administration.

---

Reliable methods of contraception are:

- hormonal methods or intrauterine device in use  $\geq$  90 days prior to study product administration; or
- barrier methods plus spermicide in use at least 14 days prior to study product administration.
- partner has had a vasectomy at least 3 months previous to study product administration.
- Essure®

**Exception:** Sexually inactive female subjects of childbearing potential are not required to practice a reliable method of contraception and may be enrolled at the investigator's discretion provided that they are counseled to remain sexually inactive for the duration of the study and understand the possible risks involved in getting pregnant during the study. An abstinent female must agree that if she becomes sexually active during the study she will use an acceptable form of contraception.

6. Subjects must be able to have  $\geq$  60 days washout from prohibited medications:
  - Masoprocol
  - 5-Fluorouracil
  - Cyclosporin
  - Retinoids (oral and topical)
  - Trichloroacetic Acid/Lactic Acid Peel
  - 50% Glycolic Acid Peel
  - Topical or systemic diclofenac, celecoxib or any other NSAID (however daily low-dose aspirin is allowed, as long as the subject has been on a stable dose,  $\leq$  100 mg once a day, for 60 days prior to the start of the study.) Note: Subjects may use acetaminophen/paracetamol as needed
  - Photodynamic therapy
  - Topical or systemic immunomodulating agents
  - Systemic, topical or intralesional interferon
  - Imiquimod (Aldara, Zyclara)
  - Topical ingenol mebutate (Picato)
  - Topical tacrolimus
  - Topical pimecrolimus
  - Sirolimus
  - Intralesional BCG
  - Topical coal tar products
  - Topical or systemic corticosteroids (nasal and inhaled steroids are allowable)
7. Subjects must agree not to use any product on the treatment area during the entire course of study except for Investigator-approved cleanser, sunscreen, wash, and non-medicated make-up. Subjects should continue to use these Investigator-approved products for the duration of the study and should avoid any changes in these consumer products.
8. Subjects must be willing to comply with sun avoidance measures for the face including use of Investigator-approved sunscreen and/or hats, have limited sun exposure time, and have no tanning bed use.

---

9. Subjects must be in good general health as determined by the Investigator and supported by the medical history, and normal or not clinically significant abnormal vital signs (blood pressure and pulse). Subjects are eligible if:

- Systolic blood pressure (BP) < 160 and > 85 mmHg
- Diastolic BP < 100 and > 50 mmHg

**Exclusion:**

1. Known or suspected hypersensitivity to any non-steroidal anti-inflammatory drugs (NSAID) or any component of the formulation of the study medication, including a history of asthma, urticarial, or other allergic-type reactions after taking aspirin or other NSAIDs.
2. Known or suspected allergy to sulfonamides.
3. Clinical evidence of severe, uncontrolled autoimmune, cardiovascular, gastrointestinal, hematological, hepatic, neurologic, pulmonary or renal disease.
4. Recent (within 6 months) or planned coronary artery bypass graft surgery.
5. Significant history (within the past year) of alcohol or drug abuse.
6. Participation in any clinical research study within 30 days of the Baseline Visit.
7. Concomitant use of cosmetics or other topical drug products on or near the selected treatment area except for Investigator-approved cleanser, sunscreen, wash, and non-medicated makeup.
8. Cosmetic or therapeutic procedures (e.g. laser, peeling, photodynamic therapy) within 2 weeks and within 2 cm of the selected treatment area.
9. Other skin conditions within the selected treatment area (e.g. rosacea, psoriasis, atopic dermatitis, eczema, basal or squamous cell carcinoma or albinism).
10. Use of sun lamps, tanning beds, and tanning booths during the 14 days prior to the Baseline Visit or planned use during the study.
11. Any systemic cancer therapy or diagnosis within 6 months of the Baseline Visit.
12. Females who are pregnant or lactating or planning to become pregnant during the study period.
13. Subjects may not have a personal relationship with any member of the study staff or be part of the staff at the medical practice.
14. Subjects who are unable to comply with the study requirements for any reason.

---

**Investigational Product, Dose and Mode of Administration:**

This is a multi-center, randomized, double-blind, parallel group, Vehicle-controlled study. Subjects, who are at least 18 years old, diagnosed with AK of the face and/or scalp will be randomized to treatment with one of the following:

1. DFD-07 (celecoxib) Cream, 1.25% once daily in the evening/PM and Vehicle for DFD-07 (celecoxib) Cream, 0% once daily in the morning/AM for 12 weeks.
2. DFD-07 (celecoxib) Cream, 2.5% once daily in the morning/AM and evening/PM for 12 weeks.
3. DFD-07 (celecoxib) Cream, 2.5% once daily in the evening/PM and Vehicle for DFD07 (celecoxib) Cream, 0% once daily in the morning/AM for 12 weeks.
4. Vehicle (celecoxib) Cream, 0% once daily in the morning/AM and evening/PM for 12 weeks.

---

The investigational products will be applied twice daily for 12 weeks to cover the entire lesional area on the face and/or scalp. The maximum amount of study product applied will be 0.5 g per application to a 5 cm x 5 cm area (single contiguous area) on the face and/or scalp for a maximum dose of 1.0 g per day.

---

**Duration of Treatment and Study:**

Subjects will treat the affected area for a maximum of 12 weeks. The total expected study duration is 24 weeks including the Screening and Follow-Up Visits.

---

**Reference and Control Products, Dose and Mode of Administration:**

Subjects will be treated with either topical DFD-07 (celecoxib) Cream containing 1.25% or 2.5% or the matching topical Vehicle Cream.

---

**Criteria for Evaluation:****Safety criteria:**

Safety assessments will be performed at each visit to include vital signs (blood pressure, pulse rate), urine pregnancy tests for women of child bearing potential, local cutaneous tolerability evaluation (including erythema, edema, weeping/exudate, flaking/scaling/dryness, scabbing/crusting, erosion/ulceration, vesiculation/blistering), and collection of adverse event data.

For the safety analysis, only treatment-emergent adverse events (TEAEs) will be analyzed. Treatment-emergent adverse events will include any adverse event (AE) occurring during the treatment period. For pre-existing conditions, any condition that worsens during treatment will be considered treatment-emergent.

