### 4.2 Discussion of Design

The study consists of three phases: Screening (up to 60 days), Treatment (12 weeks) and Follow-Up (4 weeks). In Groups 2 and 4, the randomized investigational products will be applied twice daily for 12 weeks to cover the entire single contiguous 5 cm x 5 cm (25 cm^2) lesional area on the face and/or scalp. In Groups 1 and 3, the randomized active DFD-07 (celecoxib) Cream product will be applied only in the evening, while the Vehicle for DFD-07 Cream will be applied in the morning to keep the blinding between groups.

Subjects in all the groups will undergo a further 4-week treatment-free period from Week 12 to Week 16 (End of Study).

The investigational products will be applied twice daily for 12 weeks to cover the entire lesional area (5 cm x 5 cm) on the face and/or scalp identified by the Investigator for treatment. The dose for the study product will be a maximum of 0.5 g per application to the entire 5 cm x 5 cm area on the face and/or scalp for a maximum dose of 1.0 g per day.

Subject visits are scheduled at Screening (Visit 1), Baseline (Visit 2 - Day 1), and Weeks 4 (Visit 3), 8 (Visit 4), 12 (Visit 5) and 16 (Visit 6). Clinical determinations of efficacy will be conducted based on clinically visible or palpable lesions of AK in the treated areas at Weeks 4, 8, 12 and 16 in comparison to Baseline. Comparisons will be made between the different strengths and dosing regimens of DFD-07 (celecoxib) Cream and Vehicle Cream.

Local cutaneous tolerability will be determined at Visits 2 – 6 for the entire treated area. Other safety assessments include physical examinations (HEENT, lungs, heart, abdomen, skin,

---

neurologic), laboratory assessments, electrocardiogram (EKG), vital signs (blood pressure, pulse rate), urine pregnancy tests, and collection of adverse event data.

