## 7.6 Early Withdrawal of Subjects

1. Subjects should be withdrawn from the study if they no longer wish to participate, are being uncooperative, or if the Investigator feels that it is in the best interest of the subject to withdraw.
2. Subjects with protocol deviations or for whom it is discovered should have been excluded should not be withdrawn unless there is a safety concern. The protocol deviation should be recorded in the subject's source documents and the eCRF.
3. If during the course of treatment a subject experiences a cardiovascular or hematologic AE (including abnormal laboratory values) of Common Terminology Criteria for Adverse Events (CTCAE) Version 4.02 Grade 2 or higher, the study product will be discontinued and the subject will be withdrawn from the study.
4. Subjects who experience an AE resulting in or requiring discontinuation of study product use should be encouraged to be followed until the AE is resolved or stabilized.
5. If a female subject becomes pregnant during the study, study product will be discontinued immediately and she will be followed through the pregnancy and delivery. Details of the pregnancy, delivery and health of the infant should be recorded on the Pregnancy Surveillance Form. The Sponsor will be notified immediately after the subject is detected to be pregnant.
6. At the time of study discontinuation, the Investigator will record the reason for early withdrawal, date of last study product application, date of last visit or contact, collect adverse event data, and, if possible, perform all End of Study Visit specific evaluations. Every attempt should be made to contact subjects who are lost-to-follow-up. At least three attempts must be documented in the subject's source document, including the use of at least one certified letter. Any contact, either direct or indirect, should be made with the purpose to document the final status of the subject with regard to safety. Subjects who withdraw early will not be replaced.

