## 7.10 Study Schedule

A Study Schedule Chart can be found on page 9. There are at least 5 study visits; Screening (Visit 1), Baseline (Visit 2, Day 1), Week 4 (Visit 3), Week 8 (Visit 4), Week 12 (Visit 5-End of Treatment) and 4 Weeks Post-Treatment (Visit 6 – End of Study). The Screening Visit and Baseline/Day 1 Visit may be combined into a single visit if no wash-out is required. The visit window is  $\pm 5$  days for Weeks 4, 8, 12 and 16. Visits 1 and 2 cannot be separated by more than 60 days.

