#### **7.10.5 Visit 5 – Week 12/End of Treatment Visit (Allowed visit window is $\pm$ 5 days)**

1. Evaluate treatment and protocol compliance and record any deviations. This includes a review of the diary card for number of applications and missed applications.
2. Investigator is to document the number and location of the lesions with in the treatment area and on a grid foil. One copy of the grid foil should be inserted into the subject's source document.
3. Collect vital signs (blood pressure and pulse rate).
4. Perform a physical examination (HEENT, lungs, heart, abdomen, skin, and neurologic).
5. Perform a 12-lead EKG.
6. Collect blood (2/3 tablespoon) and urine for hematology/chemistry/urinalysis safety labs.
7. Conduct a urine pregnancy test for all females of child bearing potential.
8. Collect AE data. This includes a review of the diary card for potential AEs.
9. Update concomitant medications data.
10. Dispense diary and review instructions. Advise subjects that if they still have unreturned tubes of study product, they are not to use any of the study products after this visit.

11. Weigh tubes when they are collected.
12. Schedule next visit.
13. Complete eCRF.

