#### **7.10.6 Visit 6 – Week 16/End of Study Visit (Allowed visit window is $\pm$ 5 days)**

1. Evaluate protocol compliance and record any deviations.
2. Investigator is to document the size and location of the lesions with in the treatment area and on a grid foil. One copy of the grid foil should be inserted into the subject's source document.
3. Collect vital signs (blood pressure and pulse rate).
4. Conduct a urine pregnancy test for all females of child bearing potential.
5. Collect AE data. This includes a review of the diary card for potential AEs.
6. Complete eCRF.

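### The only TEAE wording ends with treatment, so AEs starting in the Week 12–16 follow-up appear to be left out of Tables 14.3.1.1–14.3.1.3

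*Protocol*

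**What the plan says.** The protocol synopsis (Safety criteria) says that "only treatment-emergent adverse events (TEAEs) will be analyzed". It then gives the only description of the term in the text available: "Treatment-emergent adverse events will include any adverse event (AE) occurring during the treatment period". The next sentence, on pre-existing conditions, likewise refers to worsening during treatment. The protocol's abbreviation list expands the acronym and adds nothing on timing.

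The Synopsis (Methods) and Protocol 4.2 set out a 12-week treatment phase and a separate 4-week follow-up phase, and describe Weeks 12 to 16 as free of treatment. At Visit 5, labelled End of Treatment, subjects with unreturned tubes are told that "they are not to use any of the study products after this visit" (Protocol 7.10.5).

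AE collection continues. Protocol 8.1 runs it from the start of treatment to the Week 16 visit, and the Visit 6 procedures include: "Collect AE data. This includes a review of the diary card for potential AEs" (Protocol 7.10.6).

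Protocol 11.5.3 and SAP 2.5.1 summarize treatment-emergent AEs by arm and list all AEs noted in the study. In SAP 4.1, Tables 14.3.1.1–14.3.1.3 are titled as treatment-emergent. Tables 14.3.1.4 (AEs leading to discontinuation) and 14.3.1.5 (SAEs) are not.

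**The concern.** The stated objective covers safety as well as efficacy by dose, and it names the 4-week follow-up (Protocol 3; SAP 1.3). If treatment-emergent means onset within the treatment phase, the three main between-arm AE tables cover a shorter span than the one over which sites must collect AEs. A reader who wanted to compare arms on AEs starting after treatment would have to count them from subject listings.

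There is a second, smaller gap. The treatment period is not defined in days or relative to last dose. For a subject who stops product early, the text does not say whether it ends with the last application or at the scheduled Week 12 visit. Two programmers could therefore build different TEAE tables from the same data.

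**Working it through.** The plan states no figure to reproduce. The check sets the texts side by side and then works out how much AE observation time is involved.

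**Text check**

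| Question | Source | Answer |
|---|---|---|
| Which AEs are treatment-emergent? | Synopsis, Safety criteria | Those during the treatment period; pre-existing conditions that worsen during treatment |
| Is Week 12–16 part of treatment? | Synopsis Methods; Protocol 4.2, 7.10.5 | No, it is a separate phase without treatment |
| Until when are AEs collected? | Protocol 8.1, 7.10.6 | Week 16 |
| Which AEs are summarized by arm? | Protocol 11.5.3; SAP 2.5.1; Tables 14.3.1.1–14.3.1.3 | Treatment-emergent AEs |
| Does the SAP text available give its own window? | SAP 2.5.1 | No |
| Which AEs are listed? | SAP 2.5.1; Listing 16.2.7.1 | All noted during the study |
| Are local reactions covered at Week 16? | SAP 2.5.2; Tables 14.2.6.x and 14.3.3 | Yes, tabulated by visit |

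Read together, an AE with onset in follow-up reaches the listing but meets no stated condition for entry to Tables 14.3.1.1–14.3.1.3. Of the five AE tables, 14.3.1.1–14.3.1.5, three carry the treatment-emergent limit in the title.

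**Observation time**

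Inputs: end of treatment at Week 12 = day 84; end of study at Week 16 = day 112, both counted from first application; window ±5 "days for Weeks 4, 8, 12 and 16" (Protocol 7.10).

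Follow-up share = (Week 16 day − Week 12 day) / Week 16 day.

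- Nominal: (112 − 84)/112 = 28/112 = 25%, the same as 4/16 weeks.
- Week 12 visit between 84 − 5 = 79 and 84 + 5 = 89; Week 16 visit between 112 − 5 = 107 and 112 + 5 = 117.
- Shortest follow-up: (107 − 89)/107 = 18/107 = 16.8%.
- Longest follow-up: (117 − 79)/117 = 38/117 = 32.5%.

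These shares apply to a subject who completes both visits within their windows.

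**Onset dates**

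SAP 2.10 leaves a start date missing when the year is unknown, so such an AE cannot be placed before or after last dose. When only the day is unknown, outside the month of first dose, it is set to 01. An AE in the month of last application then falls on or before the last dose date.

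**The case against.** The best reply is that the text is less firm than this reading. The synopsis says what TEAEs will include; it does not literally say they are limited to that. SAP 2.5.1 reserves listing-only treatment for procedure-related AEs before dosing, which hints that everything after dosing was meant to be summarized. The definition may also sit in the table shells, kept in a separate file (SAP 4.3) that was not available, or be settled in the signed Documentation of Statistical Decisions before lock (SAP 2.1). All of this stands as a limit on certainty: it cannot be said that the shells leave the rule unchanged. It does not remove the point. No text available extends the window, and if the wider window was intended, the synopsis should not say that only events of the treatment period are analyzed.

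A second reply is that an on-treatment window is a legitimate choice and that little is lost: a topical product, four weeks off drug, local reactions tabulated by visit, and AEs that began on treatment still counted. That is fair, and it holds the priority down. A flagged table, however, shows the on-treatment view and the follow-up view together.

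A reader might go further and infer that a quarter of AEs are lost, that follow-up AEs go unreported, or that follow-up SAEs are dropped from the summaries. The documents support none of these. The 25% is time, not events. All AEs are listed. The titles of Tables 14.3.1.4 and 14.3.1.5 carry no treatment-emergent limit and most naturally cover all AEs; only the synopsis sentence conflicts with that.

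**Conclusion.** The point holds on the natural reading of the text available. AEs with onset in follow-up are collected and listed but left out of the overall, severity and relationship tables by arm. The main effect is on non-serious AEs other than the seven local reactions.

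The size is 25% of AE collection time nominally, with a range of 16.8% to 32.5%. The number of events cannot be derived from the documents.

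The conclusion assumes that the treatment period means the 12-week treatment phase and that the unseen shells do not define the term otherwise. The status of AEs after early stopping is unclear under any reading. Priority is minor to moderate, and no efficacy inference is affected.

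**What to change.** 1. In SAP 2.5.1, define a TEAE as an AE with onset or worsening from first application through the Week 16/End of Study visit or last contact. Align the synopsis sentence at the next protocol amendment; a change there needs sponsor and IRB agreement (Protocol 7.7), and the SAP definition need not wait for it.
2. Present Tables 14.3.1.1–14.3.1.3 with a flag separating onset on or before the last dose date from onset after it. This also settles the early stoppers.
3. State that Tables 14.3.1.4–14.3.1.5 cover all AEs from first application through Week 16. Procedure-related AEs before dosing stay in Listing 16.2.7.4.
4. State that an AE whose onset date remains missing under SAP 2.10 counts as treatment-emergent and on-treatment unless other data show otherwise.

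The cost is one definition, one programming flag and two sentences. No new data are needed: SAP 2.4.2 already uses the last dose date for every subject's exposure days, and for subjects who discontinue, Protocol 7.6 has the investigator record the "date of last study product application".

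There are two downsides. Tabulated incidence rises slightly in all arms, and onset days imputed to 01 lean the split toward on-treatment, which a table footnote should say.
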